#### **6.10.2.2. Incidence rate of aetiology confirmed, probable and/or clinically suspected meningitis**

Final classification (based on second line laboratory results and after external panel of experts review) will be used to compute IR. The meningitis cases will be analysed grouped as follows:

- Probable meningitis,
- Aetiology confirmed, and/or probable meningitis,
- Aetiology confirmed, probable and/or clinically suspected meningitis.

The IR (and 95% CI) of each definition of meningitis cases will be estimated with the same approach as for the co-primary endpoints (described in Section [6.9.3.2](#)).

For IR following EPI vaccine, the at-risk period applied will be 12 months after each vaccine administration and same approach as described in section [6.9.3.3](#) will be used to compute IR for children less than 5 years.

### **6.10.3. Cerebral malaria**

The IR (and 95% CI) of cerebral malaria will be estimated with the same approach described in Section [6.9.3](#). Incidence following EPI vaccine or virtual vaccination with a 12 month risk period will be derived and Time-to-Onset will be computed.

### **6.10.4. Analysis of risk factors**

Analysis of potential risk factors of the below secondary safety endpoints will only be done on hospitalised events from ATP-Active surveillance for IR following EPI vaccine or virtual vaccination on primary schedule and virtual secondary schedule only (ie: primary schedule and virtual dose 4 only) by means of univariate and multivariate Poisson regression models for the following confirmed (final diagnosis) endpoints:

- *Each AESI separately*

- Aetiology confirmed meningitis,
- Cerebral malaria,
- Death.

For those endpoints, if possible, a model with study site considered as random effect will be performed as sensitive analysis. The methods are described in section [7.5.1](#) and in section [7.5.2](#).

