9.7.7.2. Statistical approach

Incidence rates for each event will be calculated by dividing the number of cases by person-time as defined in [Table 8](#). Of note, for cerebral malaria, incidence following DTP/HepB/Hib vaccine or virtual vaccination will be derived and Time-to-Onset will be computed (see Section [9.7.5.2.1](#)).

CONFIDENTIAL

115055 (EPI-MALARIA-002 VS AME)
Protocol Amendment 7 Final

For analyses using detailed information from the eCRF, children whose parents do not consent for them to take part in the active surveillance groups will not be included in the denominator.

Table 8 Incidence rate and prevalence calculations for other objectives (children enrolled in active surveillance)

Endpoints	Numerator	Denominator
Any malaria	# cases of any malaria Source: Outpatient visits and hospitalisations at all health care facilities	Person-years contribution of enrolled children
Any P. falciparum malaria	# cases of any malaria due to P. falciparum Source: Outpatient visits and hospitalisations at all health care facilities	Person-years contribution of enrolled children
Severe malaria	# cases of severe malaria Source: Hospitalisations	Person-years contribution of enrolled children
Severe P. falciparum malaria	# cases of severe malaria due to P. falciparum Source: Hospitalisations	Person-years contribution of enrolled children
Cerebral malaria	# cases of cerebral malaria Source: Hospitalisations	Person-years contribution of enrolled children
Anaemia in hospitalised children	# cases of anaemia Source: Hospitalisations	Number of enrolled children
Death – all cause	# deaths (due to any cause) Source: Scheduled home visits; outpatient visits and hospitalisations at all health care facilities; completion visit; HDSS or equivalent surveillance system register	Person-years contribution of enrolled children
Malaria attributed deaths	# deaths with malaria listed as a contributing cause Source: Scheduled home visits; outpatient visits and hospitalisations at all health care facilities; completion visit; HDSS or equivalent surveillance system register	Person-years contribution of enrolled children
Hospitalisation - all cause	# of children hospitalised during study period Source: Hospitalisations	Person-years contribution of enrolled children

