## 6.9.3. Incidence of co-primary endpoints

### 6.9.3.1. Description of the events

The occurrence of the following endpoints will be regularly (every 6 months) reported in progress reports [[Progress Report](#)] on the total enrolled cohort for hospitalised cases and outpatient visits when applicable:

- Each AESI according to site diagnosis,
- Other AE leading to hospitalisation or death, according to site diagnosis
- First line laboratory meningitis diagnosis according to site diagnosis following protocol definition (i.e. Bacterial confirmed meningitis, probable meningitis, clinically suspected meningitis).
- Malaria cases reported during outpatient visit or at hospital:
  - Clinically diagnosed Malaria
  - Any uncomplicated malaria (including *P. falciparum* malaria)
  - Any severe malaria (including *P. falciparum* malaria)
  - Severe *P. falciparum* malaria
  - Severe *P. vivax*
  - Cerebral malaria

- Fatal malaria cases
- Death reported at hospital or at home classified by MedDRA PT from study conclusion.

The number of subjects (%) reporting at least once each endpoint as well as the total number of events listed above and the number of associated outpatient visits/hospitalisations will be presented for both AS and EHS by EPI vaccination status and by gender. MedDRA SOC and PT level will be displayed for those safety endpoints.

Progress reports will include individual listings and statistical tables. The same tables and listings will also be presented for the final report.

Descriptive data in the progress report will also be presented:

- The demographic census will be presented by study site and by age group according to gender and overall.
- The number of subjects enrolled will be presented by study site, by study group and according to EPI vaccination status.
- The evolution of enrolment will be presented separately for each study group.
- Population characteristics (age at informed consent, gender) will be described by study group according to EPI vaccine received.
- The number and percentage of subjects who received the EPI vaccine doses will be summarised for EPI vaccinated subjects by each study group according to gender and overall.

And descriptive analysis of quality indicators (see section 6.10.7) will be done:

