Any malaria	# cases of any malaria during the follow-up time of each analysis Source: Outpatient visits and hospitalisations at all health care facilities	Person-years contribution of enrolled children during the follow-up time of each analysis
Any P. falciparum malaria	# cases of any malaria due to P. falciparum during the follow-up time of each analysis Source: Outpatient visits and hospitalisations at all health care facilities	Person-years contribution of enrolled children during the follow-up time of each analysis
Severe malaria	# cases of severe malaria during the follow-up time of each analysis Source: Outpatient visits and hospitalisations at all health care facilities	Person-years contribution of enrolled children during the follow-up time of each analysis
Severe P. falciparum malaria	# cases of severe malaria due to P. falciparum during the follow-up time of each analysis Source: Outpatient visits and hospitalisations at all health care facilities	Person-years contribution of enrolled children during the follow-up time of each analysis
Cerebral malaria	# cases of cerebral malaria during the follow-up time of each analysis Source: Hospitalisations	Person-years contribution of enrolled children during the follow-up time of each analysis
Death – all cause	# deaths (due to any cause) during the follow-up time of each analysis Source: Regular home visits; outpatient visits and hospitalisations at all health care facilities, completion visit; HDSS register	Person-years contribution of enrolled children during the follow-up time of each analysis
Malaria attributed deaths	# cases of deaths with malaria listed as a contributing cause during the follow-up time of each analysis Source: Regular home visits; outpatient visits and hospitalisations at all health care facilities, completion visit; HDSS register	Person-years contribution of enrolled children during the follow-up time of each analysis
P. falciparum Malaria attributed deaths	# cases of deaths with malaria due to P. falciparum listed as a contributing cause during the follow-up time of each analysis Source: Regular home visits; outpatient visits and hospitalisations at all health care facilities, completion visit; HDSS register	Person-years contribution of enrolled children during the follow-up time of each analysis

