**Table 5 List of analyses by endpoints**

	Description of events	Incidence following primary and secondary schedule	Incidence for children < 5 years	Cumulative probability	Analysis of risk factors on IR following primary/secondary schedule	Incidence following:	Analysis of risk factors on IR	Prevalent rate
AESI according to Final diagnosis								
AESI (by MedDRA SOC & PT)	○/●	-	-	-	-	-	-	-
AESI by case definition as listed in CRF	○/●	○	●	○	○*	-	-	-
AESI grouped by body-system	○/●	○	●	-	-	-	-	-
Other AE leading to hospitalization or death according to Final diagnosis								
Other AE leading to hospitalisation or death (by MedDRA SOC & PT)	○/●	-	-	-	-	-	-	-
Other AE leading to hospitalisation or death (Aggregated)	-	○	●	-	-	-	-	-
Meningitis according to Final diagnosis								
Aetiology confirmed meningitis	○/●	○	●	○	○*	-	-	-
Aetiology confirmed, and/or probable meningitis	○/●	○	●	-	-	-	-	-
Probable meningitis	○/●	○	●	-	-	-	-	-
Aetiology Confirmed and/or probable and/or suspected meningitis	○/●	○	●	-	-	-	-	-
Malaria according to Final diagnosis								
Any Malaria	○/●	-	-	-	-	○	○	-
P. falciparum Malaria	○/●	-	-	-	-	○	○	-
Severe Malaria	○/●	-	-	-	-	○	○	-
P. falciparum severe Malaria	○/●	-	-	-	-	○	○	-
Cerebral Malaria	○/●	○	●	○	○*	○	○	-
Death (overall and by gender)								
Death all cause	○/●	○ a	●	○	○*	○	-	-
Death due to an AESI (all grouped)	○/●	○ a	●	○	-	○	-	-
Death due to another AE (all grouped)	○/●	○ a	●	○	-	○	-	-
Death due to meningitis	○/●	○ a	●	○	-	○	-	-
Death due to malaria (including P. falciparum malaria)	○/●	○ a	●	○	-	○	-	-
Death due to P. falciparum malaria	○/●	○ a	●	○	-	○	-	-
Hospitalisation								
Hospitalisation all causes	○/●	○ a	●	○	-	○	-	-
Hospitalisation due to malaria (including P. falciparum malaria)	○/●	○ a	●	○	-	○	-	-
Hospitalisation due to P. falciparum malaria	○/●	○ a	●	○	-	○	-	-
Anaemia								
Anaemia	○/●	-	-	-	-	-	-	○
Severe anaemia	○/●	-	-	-	-	-	-	○
Febrile convulsions								
Febrile convulsions	○/●	○	-	-	-	-	-	-
Surveillance indicator								
Foot positional deformations as a birth defect	○	-	-	-	-	-	-	-
Abscess at the injection site	○	-	-	-	-	-	-	-
● Analysis to be done for AS and EHS			Primary objective					
○ Analysis to be done only for AS			Secondary Safety objective					

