### **7.2.3. Date of occurrence**

The dates of occurrence of events are defined as follows depending on the endpoint:

- Suspected or confirmed AESI and meningitis reported at hospital:
  - Onset date of event
- Suspected AESI and suspected meningitis reported during outpatient visit (see section [7.3](#) for worst case allocation sensitivity analysis):
  - Admission date at outpatient visit
- Other AE leading to hospitalisation or death:
  - Onset date of event if AE is the primary diagnosis
  - Admission date at hospital otherwise
- Suspected or confirmed malaria cases:
  - Onset date of event for hospitalised cases
  - Admission date at outpatient visit otherwise
- Death:
  - Date of death reported in study conclusion

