**7.2.12. Deaths**

- Deaths – all causes  
A fatality (of any cause).
- Malaria attributed deaths (including *P. falciparum* malaria)  
A fatality for which malaria (including *P. falciparum* malaria) is listed as a contributing cause of death.
- *P. falciparum* malaria attributed deaths  
A fatality for which
  - Malaria is listed as a contributing cause of death
  - And the malaria type is identified as *P. falciparum*.
- Deaths attributed to an AE
- Deaths attributed to an AESI
- Meningitis attributed death

*Of note, as cause of death is a free text reported by the investigator on the Study Conclusion form, a specific guideline explaining the process to retrieve the above categories was prepared (EPI-MALARIA-002 VS AME (115055) General study information study specific coding term retrieval and supply for MedDRA coding\_version 2.0\_20190108)*

Number of outpatient visits per centre

The number of outpatient visits per centre will be computed as the sum of outpatient visits that occurred for the children enrolled in the same centre.

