**Table 6 Covariates used in the models according to each endpoint**

Endpoint	Population	Model	Forced-In covariates	Individual level covariates		
				General covariates	Comorbidity	Malaria specific covariates
AESI	AS ATP	Fixed effect Poisson models	o	o	o	
Meningitis	AS ATP	Fixed effect Poisson models	o	o	o	
Cerebral malaria	AS ATP	Fixed effect Poisson models	o	o	o	
Malaria	AS ATP	Fixed effect Poisson models	o	o	o	o
Deaths (All causes)	AS ATP	Fixed effect Poisson models	o	o	o	o

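### SAP 6.10.4 limits its risk-factor models, Death included, to hospitalised events, while Tables 5 and 6 assign that model to all-cause death in active surveillance; the passages need reconciling

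*SAP*

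**What the plan says.** SAP 6.10.4 sets out the risk-factor models for incidence after EPI or virtual vaccination. Its opening sentence reads "Analysis of potential risk factors of the below secondary safety endpoints will only be done on hospitalised events from ATP-Active surveillance", and it names four endpoints: each AESI separately, aetiology-confirmed meningitis, cerebral malaria and death. The last carries no qualifier.

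Two summary tables cover the same analysis. In SAP Table 5 the row "Death all cause" is marked in the column for risk factors on incidence following the primary and secondary schedules, including the sensitivity analysis with site as a random effect. SAP Table 6 has a row for deaths from all causes, with a fixed effect Poisson model in the active surveillance ATP cohort. Neither table mentions a hospital limit for death.

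The rest of the SAP treats death without regard to place:
- Section 7.2.12 defines all-cause death as any fatality.
- Table 4 in 6.11.2 gives its origin as "Source: Regular home visits; outpatient visits and hospitalisations at all health care facilities, completion visit; HDSS register".
- Section 6.9.3.1 lists "Death reported at hospital or at home classified by MedDRA PT from study conclusion".
- Section 7.2.3 dates it by "Date of death reported in study conclusion".
- Section 6.10.5, on incidence of death, foresees deaths at home.

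**The concern.** Two numerators are possible for the Death model: deaths during a hospitalisation (6.10.4 as worded) or all deaths in the cohort (Tables 5 and 6 read with 7.2.12). No passage says which applies, and none gives the tables precedence over 6.10.4 or the reverse. SAP section 9, on changes from the protocol, is silent on this.

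The choice matters because this is the only regression left with death as its outcome. The other-secondary risk-factor models in 6.11.2 now cover any, severe and cerebral malaria only, and Table 5 shows a dash for all-cause death in that later column. Protocol 9.9 also calls all-cause mortality an important endpoint, because cause of death is hard to establish in the field and some severely ill children may die before they can be taken to hospital. A hospital-only count would leave those deaths out.

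Section 7.5.3.2.1 forces usual place of care and distance to the provider into the model. Both could influence whether a dying child reaches a facility, so on the literal reading their rate ratios could mix the risk of dying with the chance of dying in hospital.

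**Working it through.** The documents state no figure on this point and do not split deaths by place, so the check is mainly textual.

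**Step 1: is it the same analysis?** Section 6.10.4 models incidence following the primary and virtual secondary schedules. The Table 5 column is headed in the same terms, and its random-effect marker matches the sensitivity analysis named in 6.10.4. The incidence of death on those schedules is described in 6.10.5, which allows for home deaths. The model and the rate it is meant to explain would therefore have different numerators if 6.10.4 were followed literally.

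**Step 2: which deaths would be lost?** Protocol 9.1 defines hospitalisation as at least one night at a health care facility. Deaths at home, on the way, or before one night has passed would not qualify.

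**Step 3: what happens to the denominator?** SAP Table 2 stops follow-up at the date of death. A child who dies at home contributes the same person-time on either reading. Only the event count changes, so on the literal reading an out-of-hospital death acts as censoring.

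**Step 4: what could that do to a rate ratio?** Take a crude two-group contrast, children living far versus near. Let h be the share of deaths that occur in hospital, and q = h(far) / h(near). With person-time unchanged,

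modelled ratio = [h(far) × rate(far)] / [h(near) × rate(near)] = true ratio × q.

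The next figures are purely illustrative; every q and h is assumed.
- True ratio 1.0, with q = 0.8, 1.0 or 1.25: modelled 0.80, 1.00 or 1.25.
- True ratio 1.3, same q: 1.3 × 0.8 = 1.04; 1.3 × 1.0 = 1.30; 1.3 × 1.25 = 1.63 (rounded).
- With q = 1 there is no bias, but the log-scale interval widens by about 1/√h: 1.83, 1.41 or 1.20 times for h = 30%, 50% or 70%.

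The planned model is multivariable, so this identity shows the mechanism and is not a forecast.

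**The case against.** The strongest reply is that this is loose drafting with an evident meaning. The same sentence calls its endpoints confirmed by final diagnosis, which fits AESI, meningitis and cerebral malaria but not all-cause death. No section defines a hospitalised death. The amendment history, useful only as a hint of intent, records that models on hospitalised subjects were removed. All of that stands: counting every death is probably what is meant. But the operative sentence says only, and a programmer who follows it would drop home deaths.

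Four stronger readings are tempting, and the documents do not support them.

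- A reader might infer that the passages cannot both be implemented. That goes too far. All cause describes cause and not place. The population entry in Table 6 is the same for AESI and meningitis, so it creates no conflict by itself. Table 5 summarises earlier sections and need not repeat every limit. The programming specifications and mock tables may also settle the matter, but they are not in the documents. The difficulty comes from how the SAP defines, sources and reports all-cause death.
- A reader might infer an undeclared departure from the protocol. Protocol 9.7.6.2 plans post-vaccination risk-factor models for AESI and meningitis only. The Poisson adjustment in 9.7.7.2 does include death, and Protocol Table 8 gives "Source: Scheduled home visits; outpatient visits and hospitalisations at all health care facilities; completion visit; HDSS or equivalent surveillance system register", but it uses different time windows. Silence in SAP section 9 therefore proves little.
- A reader might infer that the distance effect will be understated. Protocol 9.9 makes a lower hospital share among distant children plausible, but the documents contain no data on it, and the direction stays open.
- A reader might extend the limit to all risk-factor models. The malaria models in 6.11.2 carry no such limit.

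**Conclusion.** The inconsistency is real and should be resolved before the final analysis. It is a stated restriction that sits badly with the SAP's own treatment of death, and not merely a missing detail. Taken literally, it removes out-of-hospital deaths from the one remaining death model while keeping those children's person-time. It would also lower the count set against the ten-case minimum of 7.5.3.4.

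Loss of events follows from the wording wherever any death occurs outside a hospitalisation, which Protocol 9.9 and SAP 6.10.5 both expect. Bias in the access-to-care rate ratios is conditional: it needs place of death to vary with distance or usual place of care after adjustment. Neither its direction nor its size can be given from the documents. The reach is limited to this secondary model. Co-primary incidence rates and the mortality rates of SAP Table 4 do not depend on it.

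**What to change.** Add one sentence to SAP 6.10.4: the restriction to hospitalised events applies to AESI, aetiology-confirmed meningitis and cerebral malaria, whereas the Death model counts all deaths in the active surveillance ATP cohort during the follow-up windows, whatever the place, dated from study conclusion as in 7.2.3. Tables 5 and 6 then stand as they are.

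If a model of hospital deaths is really intended, label it as such in both tables, list it in section 9, and say that its rate ratios describe dying in hospital and not mortality.

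The cost is a wording change. Deaths from all places are already collected and dated, and an all-cause model needs no cause of death, so no new data are required.

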#### **6.10.5. Cause of hospitalisation (including AESI, other AE, meningitis and malaria) and death**

Causes of hospitalisation (including AESI, other AE, classified by MedDRA SOC and PT level as well as meningitis and malaria) will be analysed grouped as follows:

- Hospitalisations (all causes)
- Hospitalisation for malaria (including *P. falciparum* malaria)
- Hospitalisation for *P. falciparum* malaria

In the same way, descriptive analysis of causes of death classified by MedDRA will be done overall and by gender grouped as follows:

- Deaths – all cause
- Malaria attributed deaths (including *P. falciparum* malaria)
- *P. falciparum* malaria attributed deaths
- Deaths attributed to an AESI or other AE (i.e. other than meningitis, AESI, malaria)

Descriptive analysis of the cause of hospitalisation (overall) and death (overall and by gender) will consist in computing the number of cases, person-year per 100,000 and IR (with 95% CI).

IR of all cause of hospitalisation and death will be computed following EPI vaccine or virtual vaccination (at risk period of 12 months) as described in section [6.9.3.2](#) and for children < 5 years as described in section [6.9.3.3](#). Of note, death IR per gender in children < 5 years will be computed after the first year of recruitment. Indeed, census per gender will be available after the application on field on the Protocol Amendment 4.

Note that malaria subtype will be defined using outpatient and hospitalisation visits. In case of death occurring at home malaria subtype may be unknown.

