7. BACKGROUND AND RATIONALE

7.1. Background

The devastating morbidity and mortality, particularly in children under five years of age, that results from malaria in sub-Saharan Africa (SSA) is well documented [[WHO World Malaria Report, 2012](#)]. In 2010 there were approximately 174 million cases of malaria in the African region, 98% due to *Plasmodium (P.) falciparum*, causing approximately 596,000 deaths, 91% of which were in children under five years of age [[WHO World Malaria Report, 2012](#)]. During the past decade, renewed international commitment and increased funding to scale-up proven malaria control interventions have resulted in morbidity and mortality reductions in several African countries [[Steketee, 2010](#)]. The development of efficacious malaria vaccines has been identified by national and international health authorities as a key component of a sustainable malaria control programme which will consequently have significant benefits in terms of health and the economy [[Malaria Vaccine Technology Roadmap, 2013](#)].

GSK Biologicals has developed a pre-erythrocytic *P. falciparum* malaria vaccine, RTS,S/AS01_E, for routine immunisation of infants and children living in malaria-endemic countries of SSA. RTS,S/AS01_E will be the first vaccine to be implemented for the prevention of malaria and it will be the first AS01-adjuvanted vaccine used in the paediatric population.

The vaccine antigen, RTS,S, consists of sequences of the *P. falciparum* circumsporozoite (CS) protein and hepatitis B surface antigen (HBsAg) adjuvanted with AS01_E that consists of two immune enhancers MPL (3'-O-desacyl-4'-monophosphoryl-lipid A) and QS-21 (Quillaja saponaria Molina, fraction 21), in a liposomes suspension.

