9.2.5.8. Deaths

- Deaths – all cause
A fatality (of any cause).
- Malaria attributed deaths (including *P. falciparum* malaria)
A fatality for which malaria (including *P. falciparum* malaria) is listed as a contributing cause of death. This is based on verbal autopsy using the INDEPTH Standard Verbal Autopsy Questionnaire* [[INDEPTH](#), 2003] for children who died at home or medical judgment/medical records for children who died at a primary health care facility or hospital.
- Deaths attributed to an AE
A fatality for which an AE is listed as a contributing cause of death, based on either verbal autopsy using the INDEPTH Standard Verbal Autopsy Questionnaire* [[INDEPTH](#), 2003] for children who died at home or medical judgment/medical records for children who died at a primary health care facility or hospital.

* If a site is not part of the INDEPTH network, or does not have an equivalent surveillance system in place, the INDEPTH procedures for verbal autopsy might be implemented to ensure consistency across study sites.

Deaths, including malaria attributed deaths with an uncertain diagnosis and outcome after review by the GSK safety physician will be reviewed by the expert panel to confirm the primary/secondary cause of death (see Section [9.2.7.4.4](#)).

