Because surveillance will be conducted in study areas covering mainly rural areas, children severely ill might die before being transported to hospital. In the event of death, the cause of death will be systematically documented through verbal autopsy using the INDEPTH Standard Verbal Autopsy Questionnaire* for children who died at home or medical judgment/medical records for children who died at a primary health care facility or hospital. However, ascertaining the cause of death remains a concern considering the limitation of the verbal autopsy methods in the field, this is why all-cause mortality is an important endpoint to consider in this study.

CONFIDENTIAL115055 (EPI-MALARIA-002 VS AME)
Protocol Amendment 7 Final

* If a site is not part of the INDEPTH network, or does not have an equivalent surveillance system in place, the INDEPTH procedures for verbal autopsy might be implemented to ensure consistency across study sites.

All efforts will be made to standardize data collection during EPI-MAL-002. However, due to the long duration of this study, changes in diagnostic procedures, implementation of malaria control measures such as seasonal malaria chemoprevention [WHO, 2012], and changes in treatment measures will have to be considered during the analyses of the safety and malaria data. Potential confounders will be collected at individual level during EPI-MAL-002, and at community level during EPI-MAL-005. Some subjects might also leave the study area during the study period but this is regularly documented through demographic census (scheduled at least once a year during the study periods).

To assess the vaccine effectiveness, the follow-up of an unvaccinated group during the EPI-MAL-003 study (post-implementation) is planned. However, there is an uncertainty about the recruitment of a sufficiently large unvaccinated group after the vaccine implementation of the RTS,S/AS01_E in those countries. The decision to collect information related to any malaria cases has been taken because the vaccine uptake may be very high and the number of unvaccinated children in EPI-MAL-003 may be too low to reliably estimate the direct vaccine effect. In this instance, the unvaccinated comparison group may have to be derived from EPI-MAL-002 only (estimations of the overall and total vaccine effects).

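### Malaria deaths with no species result from a visit fail the SAP's P. falciparum death definition but keep their person-time, so that secondary mortality rate is biased low by an unknown share

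*SAP*

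**What the plan says.** - **Definition.** SAP 7.2.12 sets two conditions for a P. falciparum malaria death. Malaria must be listed as contributing to the death, "And the malaria type is identified as" P. falciparum. The broader malaria-attributed death needs only the first condition.
- **Source of the species.** SAP 6.10.5 states: "Note that malaria subtype will be defined using outpatient and hospitalisation visits. In case of death occurring at home malaria subtype may be unknown". SAP 7.2.8.2 shows that species comes from a rapid test or a slide.
- **Source of the deaths.** SAP Table 4 takes P. falciparum deaths from home visits, outpatient visits, hospitalisations, the completion visit and the HDSS register. The denominator is the follow-up time of all enrolled children.
- **Cause of death at home.** Protocol 9.2.5.8 defines malaria-attributed deaths, with P. falciparum included in the term, and for children who die at home says "This is based on verbal autopsy using the INDEPTH Standard Verbal Autopsy Questionnaire".
- **Home deaths are expected.** Protocol 9.9 warns that "children severely ill might die before being transported to hospital".
- **Unknown species.** The SAP gives no separate category, bound or sensitivity analysis for it. SAP 9 also withdraws Protocol 9.7.8.1, the missing-data section. That section dealt with unconfirmed suspected events rather than species, so it would not have solved this problem, but nothing takes its place.

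**The concern.** The deaths and the species come from different sources. Deaths are found wherever they occur, including through the HDSS register. Species is known only for children who were tested at a visit. A malaria death without such a test meets the first condition in SAP 7.2.12 and fails the second, so it leaves the numerator while its person-time stays in the denominator.

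P. falciparum malaria mortality is part of a named secondary objective (SAP 3.2). Protocol 9.1.1 singles the species out because the vaccine protects only against it. SAP 6.11.1 sets these death analyses up for later comparison with EPI-MAL-003. The practical risk is misreading. With the malaria-attributed and P. falciparum rates side by side and no count of unknowns, a reader would naturally take the gap as deaths from other species, when much of it could be untested deaths.

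**Working it through.** The plan states no P. falciparum death rate, no share of deaths at home and no share with unknown species. There is no planned figure to reproduce, and what follows is the arithmetic of the definition.

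**Inputs**
- M = number of malaria-attributed deaths, taking the attribution as given.
- h = share of M with no species result. It is not in the documents; assumed values are 0.2, 0.4 and 0.6.
- p = share of M that is truly P. falciparum. Protocol 7.1 reports "approximately 174 million cases of malaria in the African region, 98% due to" this species. That is a 2010 regional share of cases, so p = 0.98 for deaths is an assumption.
- The denominator is the same in every rate, so ratios of rates equal ratios of counts.

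**1. Species-identified rate (as planned)**

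If missing species is unrelated to true species, identified P. falciparum deaths = (1 − h)pM and true P. falciparum deaths = pM. The ratio is 1 − h, whatever p is.

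Without that independence, the unknowns could all be P. falciparum, giving a ratio of 1 − h/0.98, or could include every death from another species, giving 1 − (h − 0.02)/0.98.

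| h | 1 − h | Range without independence |
|---|---|---|
| 0.2 | 0.80 | 0.796 to 0.816 |
| 0.4 | 0.60 | 0.592 to 0.612 |
| 0.6 | 0.40 | 0.388 to 0.408 |

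With p = 0.98, the independence assumption hardly matters. The size rests on h.

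**2. What h is made of**

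Suppose the untested malaria deaths are all deaths at home. Let a be the share of malaria deaths that occur at home and u the share of those with no species result from any visit. Then h = a × u, and the ratio is 1 − a × u (a and u both assumed):

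| a | u = 0.25 | u = 0.50 | u = 1.00 |
|---|---|---|---|
| 0.2 | 0.95 | 0.90 | 0.80 |
| 0.4 | 0.90 | 0.80 | 0.60 |
| 0.6 | 0.85 | 0.70 | 0.40 |

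The last column is the case in which every home death lacks a species.

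**3. Unknowns counted as P. falciparum**

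Under independence, the ratio to the true rate is [(1 − h) × 0.98 + h]/0.98 = 1 + (0.02/0.98)h = 1 + 0.0204h. This gives 1.004, 1.008 and 1.012 at h = 0.2, 0.4 and 0.6. The ceiling, reached if every non-falciparum death is among the unknowns, is 1/0.98 = 1.020.

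**4. Malaria-attributed rate already planned**

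M/(0.98M) = 1.020. Under the same assumption it lies within about 2% of the rate in step 3.

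**The case against.** **The upper bound is nearly in the plan already.** SAP Tables 4 and 5 report malaria-attributed deaths beside P. falciparum deaths, and step 4 shows that the former is within about 2% of the sensitivity rate. This stands, and it limits the harm. It does not tell the reader how many deaths lie between the two rates because the species was unknown.

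**A reader might infer that all malaria deaths at home are excluded.** The documents do not say so. SAP 6.10.5 says only that the species may be unknown. Table 4 draws on home visits and the HDSS register, and a child who died at home after a tested visit can be classified. Only deaths with no species result are lost.

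**A reader might infer that verbal autopsy cannot supply species.** That is reasonable, because the SAP takes species from visits and tests, but it is not stated. Protocol 9.2.5.8 includes P. falciparum in the definition that rests on verbal autopsy for home deaths, so the two documents need reconciling.

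**A rule may exist elsewhere.** SAP 7.2.12 refers to a separate coding guideline for retrieving the cause-of-death categories, and the mock tables and programming specifications are also separate. None is available here. The finding therefore concerns the rule as written in the SAP. That an unknown species counts as not P. falciparum follows from that rule but is not spelled out.

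**A reader might infer that the unknowns belong in the main rate.** This is debatable. Those deaths rest largely on verbal autopsy, whose limitations Protocol 9.9 acknowledges, and the 98% describes regional cases rather than deaths at these sites.

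**A reader might infer that the rate will rise in EPI-MAL-003 as care-seeking improves.** A rate that needs a tested visit could move in that way, but that study's analysis plan is not supplied, so it remains conjecture.

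**Conclusion.** The concern holds for one secondary rate. As SAP 7.2.12 and 6.10.5 are written, the P. falciparum malaria mortality rate is biased low whenever a malaria-attributed death that is truly P. falciparum has no species result from a visit. The proportional shortfall is about h. Only its direction is established; the 20% to 60% values illustrate assumed h and are not estimates. The conclusion takes malaria attribution as given and assumes that no rule outside the SAP reassigns the unknowns. All-cause mortality, malaria-attributed mortality and the co-primary endpoints are not affected, and the SAP does disclose that species may be unknown. What it lacks is a rule for those deaths and a count of them.

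**What to change.** In SAP 7.2.12 and the P. falciparum death rows of Tables 4 and 5:

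1. Keep the species-identified rate and label it as a lower bound.
2. Add a sensitivity rate that counts malaria-attributed deaths of unknown species as P. falciparum.
3. Report the number of malaria deaths with unknown species beside both rates.
4. State how long before death a visit may supply the species, and reconcile this with the verbal-autopsy wording in Protocol 9.2.5.8.

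The cost is a few sentences and one extra row per table, with no new data collection. The sensitivity rate would over-attribute by about 2% at most if the 98% case share also held for deaths. It would also carry any verbal-autopsy misclassification already present in the malaria-attributed rate, so it should be shown as a sensitivity result and not replace the identified rate.
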